In line with applicable guidelines, an IDMC is assigned to monitor the study. The IDMC consists of an independent group of clinical experts. The participants, objectives, and roles and responsibilities of the IDMC will be described in an IDMC Charter. The IDMC Charter will also define and document the content of the safety summaries, and general procedures (including communications). The first version of the charter will be finalized prior to the initiation of the study.

After the last subject in a cohort has completed his/her treatment period or has discontinued study drug, the IDMC will review the available cumulative unblinded safety data (i.e., all available data for all included subjects, including preceding cohorts) and advise the Sponsor on proceeding to the subsequent cohort (i.e., the next higher dose). Recruitment will be paused during IDMC reviews.

SAE information will be communicated to the IDMC in real time throughout the study, as per the IDMC Charter. An ad-hoc meeting can be requested by the IDMC members at any time.

Dose Escalation Stopping Criteria

In addition to the individual discontinuation criteria (see section 3.4), the following criteria apply to stopping or pausing recruitment:

1. Should an SAE indicative of acute respiratory distress or an acute systemic hypersensitivity reaction be considered by the Investigator to be related to administration of ALX-0171, recruitment in that cohort will be stopped and no further dose escalation will be done.
2. The reporting of any other SAE considered by the Investigator to be related to administration of ALX-0171 will trigger a pause in recruitment and an immediate review by the IDMC. Confirmation of the causality between the administration of ALX-0171 and the serious adverse reaction by the IDMC will result in the stopping of recruitment in that cohort and no further dose escalation will be done.

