3. In case 2 SAEs considered by the Investigator to be possibly related to administration of ALX-0171 occur in the same cohort, recruitment in that cohort will be paused to allow further investigation by the IDMC. This includes assessment of the index events as well as review of any prior similar events, after which the IDMC will issue a recommendation regarding continuation or stopping of the paused cohort. In case recruitment is reinitiated based on the IDMC recommendation, the assessment for further dose escalation will be performed by the IDMC during the planned pause after completing the cohort, when the cumulative dataset is available.
4. If 2 severe adverse events (AEs) indicative of acute respiratory distress or an acute systemic hypersensitivity reaction would occur in a particular cohort and are considered by the Investigator to be related to administration of ALX-0171, no further dose escalation will be done.

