3.4.2. DISCONTINUATION OF STUDY DRUG

A subject must be discontinued from study drug treatment if:

- The randomization code is broken prematurely by the Investigator or Sub-Investigator.
- A severe and/or serious hypersensitivity reaction to study drug occurs.
- A severe and/or serious acute respiratory distress reaction induced by study drug administration occurs.
- The subject needs to start treatment with one of the medications listed as prohibited (see section 3.3.7).
- The subject needs to start non-invasive respiratory support, invasive ventilation or HFOT at levels not enabling removal of the cannula for administration of the study drug nebulization and/or levels exceeding 2 L/kg/min. The event will be captured as an SAE and will be monitored until resolution, as described in section 4.1.4.

- If the Investigator or the Sponsor / medical monitor deems it is in the subject's best interest.
- If on Day 2 or Day 3, study drug initiation*** has not been successful after 60 minutes, study drug treatment should be discontinued (i.e., in case dose initiation was not successful on Day 2, then no dosing on Day 3 should be done).

A subject may be discontinued from study drug treatment if an SAE occurs (if considered necessary or appropriate by the Investigator).

For subjects remaining hospitalized after study drug treatment discontinuation, in-hospital post-treatment assessments will be performed in addition as specified in the [Schedule of Assessments](#). Subjects who discontinued treatment prematurely (for any reason) should also attend the FU and EOS visits.

If a subject is discontinued from the study drug, the study monitor and the Sponsor are to be informed immediately.

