Serious Adverse Events (SAEs)	
An SAE is any untoward medical occurrence (an AE) occurring at any dose of the (investigational) medicinal product, comparator or placebo that fulfils one or more of the following conditions:
 
 • Results in death • Is life-threatening 
NOTE: The term "life-threatening" in the definition of "serious" refers to an event in which the subject was at risk of death at the time of the event; it does not refer to an event which hypothetically might have caused death if it were more severe.
 • Requires inpatient hospitalization or prolongation of existing hospitalization. 
NOTE: An AE associated with a hospitalization or prolongation of hospitalization will not be regarded as an SAE, if at least one of the following exceptions is met:
 
 - Routine treatment or monitoring of the studied indication not associated with any deterioration in condition - Treatment which was elective or pre-planned, for a pre-existing condition not associated with any deterioration in condition, e.g., pre-planned prior to the start of the study hip replacement operation which does not lead to further complications. - Hospital stay of less than 12 hours. - The admission is not associated with an AE (e.g., social hospitalization for purposes of respite care). - Any admission to hospital or other institution for general care where there was no deterioration in condition. - Treatment on an emergency, outpatient basis for an event not fulfilling any of the definitions of serious as given above and not resulting in hospital admission. • Results in persistent or significant disability/incapacity. 
NOTE: Disability means a substantial disruption of a person's ability to conduct normal life's functions.
 • Consists of a congenital anomaly or birth defect (Not relevant)

Term	Definition

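### Two related severe but non-serious respiratory or hypersensitivity reactions in a cohort end dose escalation, but the protocol requires no recruitment pause and no IDMC notice before the end-of-cohort review

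*Protocol*

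**What the plan says.** The rules are in Protocol section 3.1.1, under Independent Data Monitoring Committee and Dose Escalation Stopping Criteria.

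- **Criterion 4** applies "If 2 severe adverse events (AEs) indicative of acute respiratory distress or an acute systemic hypersensitivity reaction would occur in a particular cohort". The action, where the events are "considered by the Investigator to be related to administration of ALX-0171, no further dose escalation will be done", concerns escalation alone.
- **Criterion 1** covers the same two reaction types when the event is a related SAE. There, "recruitment in that cohort will be stopped and no further dose escalation will be done".
- **Criterion 2** (any other related SAE) pauses recruitment and brings an immediate IDMC review.
- **Criterion 3** (two possibly related SAEs in a cohort) pauses recruitment, after which "the IDMC will issue a recommendation regarding continuation or stopping of the paused cohort".
- **Flow of information:** "SAE information will be communicated to the IDMC in real time throughout the study". The planned IDMC review follows the end of treatment of the cohort's last subject.

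Section 3.4.2 lists, among the reasons that oblige a child to stop study drug, "A severe and/or serious acute respiratory distress reaction induced by study drug administration occurs", with a parallel entry for hypersensitivity. It adds: "If a subject is discontinued from the study drug, the study monitor and the Sponsor are to be informed immediately". Section 4.1.3 states that severity and seriousness are different things and that a severe event may be non-serious.

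**The concern.** Criterion 4 is the only cohort-level rule that reaches a severe, non-serious, related reaction of the kinds the programme names as its potential risks. When it is met, the next dose is ruled out, but the remaining places at the current dose may still be filled. No protocol text requires the IDMC to be told before that happens.

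Whether to keep enrolling at that dose depends on whether the two children were on active drug or placebo. Sites, monitors and the study team are blinded (section 3.1.3), while the IDMC reviews unblinded data. The notice required by section 3.4.2 goes to the monitor and the Sponsor. It also depends on a drug discontinuation, so a reaction after the third and last dose may not generate it. Cohort 4 has no higher dose, so criterion 4 changes nothing there, although criteria 1 to 3 and section 3.4.2 still apply.

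**Working it through.** **1. What each trigger requires**

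| Event in a cohort | Recruitment | IDMC before end of cohort | Escalation |
|---|---|---|---|
| Related SAE, respiratory distress or systemic hypersensitivity (criterion 1) | stopped | told in real time | ended |
| Other related SAE (criterion 2) | paused | immediate review | ended if IDMC confirms causality |
| Two possibly related SAEs (criterion 3) | paused | investigates and recommends | decided by IDMC at planned pause |
| Two related severe, non-serious reactions (criterion 4) | no action stated | no notice stated | ended |

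**2. Can such a reaction be non-serious?** Section 4.1.1 makes an event serious if, among other things, it "Requires inpatient hospitalization or prolongation of existing hospitalization". ICU transfer and the start of respiratory support also trigger SAE reporting, and the Investigator may class an important medical event as serious. Section 3.6.3.8 asks for longer observation after suspected systemic hypersensitivity. These routes catch many reactions. A likely remainder is brief bronchospasm that resolves with a bronchodilator. Because inpatient stay is required on all three treatment days, such an event after dose 1 or 2 need not prolong the stay.

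**3. Cohort figures.** 15 × 4/5 = 12 active and 15 × 1/5 = 3 placebo; 4 × 15 = 60. These match the protocol.

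**4. How often could criterion 4 be met?** Section 1.2.3.2.2 reports possibly related TEAEs in 3 ALX-0171 subjects (8.6%) in the first-in-infant study, all mild. The number treated is 3 / 0.086 = 34.9, so 35, with 0 of 35 having a severe related event. The exact one-sided 95% upper limit is 1 − 0.05^(1/35) = 8.2%.

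With p the assumed chance of a severe related event in an active child, P(at least 2 of 12) = 1 − (1 − p)^12 − 12p(1 − p)^11:

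| p | P(at least 2 of 12) |
|---|---|
| 1% | 0.6% |
| 2% | 2.3% |
| 5% | 11.8% |
| 8.2% | 25.8% |

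The documents give no rate for severe, related, non-serious reactions. These values count serious and non-serious events of any type, so they overstate the gap. In the other direction, the earlier study used one low dose with salbutamol before each administration (section 1.3.3); this study escalates to 9 mg/kg without required premedication.

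**5. How many more children before a required review?** If the second affected child is the k-th of 15 enrolled, at most 15 − k remain. There are C(15,2) = 105 pairs of positions, and k − 1 of them have the later child at position k. Taking all pairs as equally likely:

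- mean k = 2 × 16 / 3 = 10.67, so the mean remaining is 15 − 10.67 = 4.33;
- median remaining 4 (k = 11: 55 of 105 pairs have k ≤ 11, 45 have k ≤ 10);
- maximum 13 (k = 2, 1 pair);
- none in 14 of 105 pairs (k = 15);
- 7 or more in 28 of 105 pairs (k ≤ 8).

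**6. Could the arm be assumed?** If the events were unrelated to arm, the pairs with at least one placebo child number 105 − C(12,2) = 105 − 66 = 39, and 39 / 105 = 37.1%. Both would be on placebo in 3 pairs (2.9%).

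**The case against.** The best defence is that criterion 4 is a deliberate middle tier: serious reactions stop or pause the cohort, severe non-serious ones cap the dose. The section heading speaks of escalation, and the synopsis names recruitment criteria and escalation criteria separately. That is a legitimate scheme, but it does not explain why the unblinded committee need not be told.

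The opposite reading is that the lead-in to the four criteria, which refers to stopping or pausing recruitment, already covers criterion 4. It may show intent, but it assigns criterion 4 no recruitment action, and the synopsis wording tells against relying on it.

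The residual case is thin. An Investigator who gave rescue treatment to avert deterioration could class the event as serious, and criterion 1 would then stop recruitment after one event. That brief bronchospasm is what remains is an inference: the adult events in section 1.3.3 were mild to moderate, and review of the first-in-infant data showed no bronchoconstrictive risk, though under salbutamol. All this narrows the gap without closing it.

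Other safeguards exist. The affected child stops drug, the Sponsor may suspend the study (section 3.5), and the IDMC may call an ad-hoc meeting. The last two are options, and the IDMC cannot act on events it has not been told of. Section 1.3.3 promises IDMC monitoring of bronchoconstriction in each cohort, but through regular reviews, which may mean only those at cohort end. The Charter governs IDMC communications and could already contain the trigger. That cannot be checked here and is the main limit on this point.

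**Conclusion.** The concern holds as a reading of the protocol text, with medium confidence. It is a modest design gap that should be closed, not a flaw that undermines the study.

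The triggering situation is uncommon. The probabilities rest on assumed rates and a zero count in 35 children. The enrolment figures assume two different affected children and equally likely positions. They bound exposure before a required review and do not count exposures averted, since the proposed change imposes no automatic pause. The 37% shows only that the arm cannot be presumed.

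According to SAP section 1, only cohort 1 was randomized (15 children) and the IDMC met on its completion. The documents do not say whether such reactions occurred, so the point concerns the plan as written and any reuse of these rules.

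**What to change.** 1. In the IDMC text of section 3.1.1, widen the real-time communication from SAEs to SAEs plus severe AEs that indicate acute respiratory distress or acute systemic hypersensitivity and that the Investigator considers related.
2. Add to criterion 4 that, once it is met, the IDMC is notified immediately and recommends whether recruitment in the cohort continues, pauses or stops. This borrows the recommendation step from criterion 3 and gives criterion 4 an effect in cohort 4.
3. Put the same trigger in the IDMC Charter, after checking whether it is already there.

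Optionally, let the lead-in to the criteria refer to dose escalation as well as recruitment.

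The cost is two short protocol edits, a matching Charter entry and a site instruction to report these few events promptly. The downside is a small reporting burden and possibly a short interruption of one cohort, because the protocol pauses recruitment during IDMC reviews.

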3.1.2. STUDY RATIONALE AND DISCUSSION OF STUDY DESIGN

Throughout the clinical program, inhalation of ALX-0171 was shown to be generally well tolerated. The encouraging results obtained in Study ALX0171-C104 (first-infant study) supported the initiation of a global Phase 2b dose-ranging study in non-Japanese infants and young children (aged 28 days to <2 years) hospitalized for RSV LRTI (N=180, study ALX0171-C201).

The present study, ALX0171-C203, is a double-blind, multiple-dose study of ALX-0171 versus placebo along with standard of care in Japanese infants and young children hospitalized for RSV LRTI. The RSV infection is confirmed by the Investigator's assessment of clinical criteria, and by virological confirmation (RSV diagnostic test).

The main objective of the study is evaluation of the safety, tolerability and PK of ALX-0171 compared to placebo. As pharmacologically active doses will be used, the antiviral effect,

clinical activity, and PD characteristics of ALX-0171 will also be evaluated, in addition to potential immunogenicity.

Study Population

The first-in-infant study ALX0171-C104 provided a first confirmation of safety and tolerability of inhaled administration of ALX-0171 in infants and young children hospitalized for RSV infection. The children enrolled in this study were, besides their RSV infection, otherwise healthy, without significant co-morbidities and with a normal gestational age. Based on the reassuring safety profile observed in study ALX0171-C104, the Phase 2 studies performed with ALX-0171 include the age range from 28 days up to <2 years, which is a highly relevant age window for this indication [11].

Considering that the Phase 2 studies are also aimed at defining appropriate dose levels for further development, co-morbidities that would confound this assessment (e.g., clinically significant heart or pulmonary diseases) are still excluded. The eligible gestational age (\geq 33 weeks) allows moderate to late ex-preterm infants to enter the study, which is an important subgroup for RSV infection [11]. Based on discussions with clinical experts, these infants are expected to behave similarly to the term infants when they have reached 28 days of age, and no other co-morbidities (which are exclusionary) are present.

The eligibility criteria in the protocol include restrictions on the type and intensity of ventilation. Only conventional oxygen supplementation through nasal cannula, head box, or face mask is allowed, since these can be continued during study drug administration (the FOX-Flamingo provides a 2 L/minute oxygen or air flow). More intense ventilation, typically used for more severely distressed infants, is part of the exclusion criteria. Critically ill infants in need of invasive ventilation or respiratory support with positive airway pressure cannot be enrolled in the study, because a different outcome and safety profile can be expected in this more severe subpopulation.

In order to enable the antiviral treatment to provide clinical benefit to the infants, the time between the start of the infection and initiation of treatment is kept as short as possible in study ALX0171-C203. The inclusion criteria therefore mandate a maximum of 4 days between the onset of symptoms of the RSV infection and screening at the hospital.

Ethnic Sensitivity

To ensure that subjects in study ALX0171-C203 are representative of the Japanese population, they are required to be born in Japan, to Japanese parents, and to have Japanese maternal and paternal grandparents.

Safety, PK/ PD characteristics, or antiviral activity have so far been evaluated in non-Japanese pediatric patients. The Sponsor expects that the combined dataset of studies ALX0171-C104 and ALX0171-C201, together with the results from Japanese study

ALX0171-C203, will enable selection of an optimal dose for future development, including in Japanese children.

Determination of Sample Size

The planned sample size of 60 randomized and treated subjects was selected to provide sufficient safety and tolerability experience with ALX-0171 in this population, to confirm the safety profile reported in studies conducted outside of Japan. The sample size also provides sufficient precision on the model estimated PK parameters, as described by Wang et al. [12], and it is expected to be informative on antiviral and clinical activity of ALX-0171.

The purpose of including placebo (in addition to standard of care) is to assist in the interpretation of results, and not for a formal statistical comparison between active and control subjects.

Dose Selection Rationale

The study drug will be administered via nebulization once daily for 3 consecutive days, in the hospital setting. The 3-day dosing regimen for ALX-0171 was based on the PD and PK properties of ALX-0171 and the current knowledge on viral kinetics and clinical management of RSV infection. The treatment period is expected to bridge the time needed for the body to mount an effective immune response that will clear the virus, and to provide the optimal individual benefit/risk balance for the subjects.

The dose range proposed to be studied in ALX0171-C203 was selected based on the results of study ALX0171-C104 (Phase 1/2a first-in-infant study), and includes the doses currently being evaluated in ongoing study ALX0171-C201 (Phase 2b dose-range finding study conducted outside of Japan). Additional details on the dose selection rationale are available in section 3.3.2.

Background Therapy

Standard-of-care therapy will be given as background therapy to all subjects in study ALX0171-C203, in addition to ALX-0171 or placebo. This is because the management of RSV in nearly all settings is supportive, and the approach is consistent with all major pediatric societies' guidelines [1, 13].

Prior or concomitant administration of palivizumab, other investigational compounds for RSV infection, or systemic corticosteroids or the initiation of inhaled corticosteroids will not be allowed; these treatments could interfere with the evaluation of ALX-0171 and are not in line with the endorsed treatments of RSV infection in the target population.

Study Assessments

The assessments which will be made in this study are standard and generally recognized as reliable, accurate, and relevant.

Safety and tolerability will be assessed through AE collection, measurements of vital signs, peripheral capillary oxygen saturation (SpO₂), physical examination, and laboratory parameters. Safety lab assessments are planned two times during the study (at screening and at the FU visit) and will be performed by the local laboratory in order to allow timely availability of the results. Furthermore, an IDMC will be involved in the regular review of the available safety data.

The systemic concentration of ALX-0171 in serum will be evaluated over time, as a surrogate for local (lung) concentrations.

Potential immunogenicity will also be assessed systemically (serum), both pre-dose and post-dose (14 days post-initial drug administration) and results will be correlated with PK, PD and safety findings.

Systemic levels of the serum biomarker Krebs von den Lungen-6 (KL-6) will be determined in left-over serum samples. Serum KL-6 was shown to indicate disease activity in various interstitial lung diseases and is believed to reflect the presence of alveolar damage [14, 15]. High serum KL-6 levels in RSV-infected infants correlate with low SpO₂ and need for oxygen administration [16]. These findings suggest that serum KL-6 is associated with the severity of RSV bronchiolitis, and that it may provide additional insight on potential treatment benefits.

The intended volume of blood to be withdrawn for each of the assessments is based on the minimum required volume for each of the respective analyses, and is in line with the volumes allowed per applicable guidelines [17-21].

Viral load will be assessed in samples obtained via nasal swabs collecting a mid-turbinate specimen, and will be quantified using plaque cultures (to evaluate replication-competent virus) and by RT-qPCR (to evaluate viral mRNA). Based on ALX-0171 mechanism of action, plaque cultures best reflects viral neutralization, whereas RT-qPCR is more sensitive, but also quantifies ALX-0171 neutralized viral particles that are unable to infect other cells, partially assembled virions, and whole and fragmented viral genome.

The clinical impact of treatment by ALX-0171 in infants and young children will be evaluated by changes in clinical symptoms (SpO₂, feeding, respiratory rate, wheezing, cough, respiratory muscle retractions, and general appearance) and subsequent calculation of composite scores, the time needed to achieve adequate feeding and oxygen saturation (clinical response) allowing for hospital discharge, the need for medical interventions, and length of hospital stay.

Based on the clinical activity parameters measured during the study, composite scores that reflect the clinical status of the subject suffering from RSV will be calculated, including the Global Severity Score, Respiratory Distress Assessment Instrument (RDAI) score, and Respiratory Assessment Change Score (RACS).

- The Global Severity Score is based on a recent clinical score that allows categorization of infants with respiratory infections on 7 different parameters: feeding intolerance, medical intervention, respiratory difficulty, respiratory frequency, apnea, general condition and fever [22, 23]. It takes into account all clinically relevant aspects of an RSV infected subject.
- The RDAI is a scoring system based on the presence and severity of wheezing and respiratory muscle retractions.
- The RACS is based on the RDAI and adds a standardized score for the change in respiratory rate.

Given the importance of timing of the administration of this antiviral compound in the time course of the RSV infection, details on the time elapsed between onset of first clinical symptoms and start of treatment with study drug will be collected and analyzed. The need for medical interventions will be documented through collection of data on the need for and level of oxygen supplementation or respiratory support, need for transfer to intensive care unit (ICU), duration of stay in ICU and overall hospital stay.

In addition to the assessments performed by healthcare professionals, the study will also collect information on how parents or caregivers perceive the clinical condition of the child through daily completion of a diary. This diary includes scoring of respiratory symptoms (cough, wheezing, trouble breathing) over the preceding 24 hours, evaluating the general health of the child by completing a Visual Analogue Scale (VAS), and answering a question as to whether the child has returned to his/her normal condition from before the onset the RSV infection. For the period after discharge from the hospital, this diary will also capture data on health care utilization and use of medication for respiratory symptoms. The diary will be completed during hospital stay and daily thereafter up to the EOS (Day 28) visit as RSV induced bronchiolitis is often associated with continuing respiratory symptoms following hospitalization.

